6.2 IMPORTANT PROTOCOL VIOLATIONS

The following table defines the different categories of important protocol violations (PVs). The right-most column describes which PVs will be used to exclude patients from the different patient analysis sets. The final decision about which patients will be excluded from analysis sets will be taken during the course of the study and at report planning meetings before database lock at the latest.

Table 6.2: 1 Important protocol violations

Category/ Code		Description	Example/Comment	Excluded from
A		Entrance criteria not met		
	A1.1	No type 2 diabetes		Efficacy
	A1.2	Patient received Trazenta® treatment before registration		All
	A1.5	Patient not treated as add-on therapy at baseline	No antidiabetic medication until start of TRZ, and start only TRZ	All
			2) Used antidiabetic medication but stopped before start of TRZ. And start only TRZ.	
			3) Used antidiabetic medication but stopped at start of TRZ. And start only TRZ.	
	A1.6	Patient start TRZ with one more OAD, but no antidiabetic medication before starting TRZ.	No antidiabetic medication until start of TRZ, but start antidiabetic medication with TRZ	Efficacy
В		Informed consent		
С		Trial medication and randomization		
C1		Incorrect study medication taken		
	C1.1	No treatment with Trazenta®		All
E		Missing data		

Table 6.2: 1(cont.): Important protocol violations

Category/ Code		Description	Example/Comment	Excluded from	
E1 No baseline value		No baseline value	No available baseline value of HbA1c for efficacy analysis	Efficacy	
G		Trial specific			
G	G1	Invalid registration			
	G1.1	No patient visit after entry	Patient made no visit after the entry	All	
	G1.2	Multiple registration	Patient who were already registered this trial with another patient ID In this case, all data for the later patient ID will not be used.	All	
	G1.3	Registration rule not followed		All	
	G1.4	Patient started Trazenta® treatment without registration period		All	
	G1.5	Not continuous investigation		All	

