6. INVESTIGATIONAL PLAN

6.1 VISIT SCHEDULE

The investigators will enrol patients who are prescribed Trazenta[®] Tablets. The observation time points will be as follows: before administration of Trazenta[®] Tablets (baseline), at 12 weeks, 26 weeks, 40 weeks, 52 weeks, 64 weeks, 78 weeks, 104 weeks, 130 weeks and 156 weeks after the start of administration, and at the time of discontinuation of administration.

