6.2 DETAILS OF STUDY PROCEDURES AT SELECTED VISITS

6.2.1 Screening and run-in periods

Before administration

The investigator will enter the following data of the patient into eCRF for registration. Preferably, registration should be executed within 14 days from the day of first administration of Trazenta® Tablets.

- Name of site, department and Investigator
- Patient ID, date of birth, gender, treatment group, start date of administration, indication, serum creatinine

The observation items are followings:

- Gender, date of birth, indication, pregnancy status, patient status (inpatient/outpatient), height, body weight, waist circumference, hypersensitivity factor, concomitant disease and medical history, pre-treatment drug, duration of type 2 diabetes mellitus, smoking status, start date of administration
- Concomitant drugs and antidiabetic therapy
- Measurement of vital signs (blood pressure, pulse rate and ECG) as safety measurement (if applicable)
- HbA1c , Fasting plasma glucose
- Laboratory tests (blood, biochemistry and urinalysis) (if applicable)

Haematology

- Leukocyte counts (WBC)
- Erythrocyte count (RBC)
- Platelet count

Blood chemistry

- AST (aspartate transaminase, SGOT)
- ALT (alanine transaminase, SGPT)
- γ-GTP (gamma-glutamyl-

- Haemoglobin (Hb)
- Haematocrit (Hct)
- HDL cholesterol (HDL)
- LDL cholesterol (LDL)
- Triglycerides (TG)
- Blood urea nitrogen (BUN)
- Amylase (AMY)

U13-1769-01

Proprietary confidential information © 2013 Boehringer Ingelheim International GmbH or one or more of its affiliated companies

Observational plan

transferase)

- Total bilirubin (T-BIL)
- Alkaline phosphatase (ALP)
- Lactic dehydrogenase (LDH)
- CK (creatine kinase)
- Total cholesterol (T-CHO)
- Lipase (LIP)
- Creatinine (CRE)
- Uric acid (UA)
- Sodium (Na)
- Potassium (K)
- Chlorine(Cl)

Urinalysis

1218.147

- Protein
- Glucose
- Urobilinogen

- Sediment
- Albumin
- Creatinine

eGFR

eGFR (mL/min/1.73 m²) =
$$194 \times$$
 Creatinine (mg/dL) $^{-1.094} \times$ Age $^{-0.287}$ For female, $\times 0.739$

6.2.2 **Treatment periods**

12 weeks, 26 weeks, 40 weeks, 52 weeks, 64weeks, 78 weeks, 104 weeks, 130 weeks, 156 weeks

The observation items are followings:

- Administration (compliance and fasting condition: 26, 78, 156 weeks)
- Concomitant drugs and antidiabetic therapy
- Adverse event
- Body weight
- Measurement of vital signs (blood pressure, pulse rate and ECG) (if applicable)
- HbA1c, Fasting plasma glucose

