6.2.3 End of trial and follow-up period

The visit at 156 weeks after starting Trazenta® Tablets treatment or the last visit before discontinuation will be the end of the PMS. There is no follow-up period.

Proprietary confidential information © 2013 Boehringer Ingelheim International GmbH or one or more of its affiliated companies

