7.3 PLANNED ANALYSES

The safety and efficacy analyses are applied only on Trazenta [®] Tablets.

The safety evaluation will be performed on the "safety set" that will include all patients who have received treatment of Trazenta[®] Tablets except those who are found to have no observation after enrolment, invalid registration, or invalid contract. The efficacy evaluation will be performed on the "efficacy set", a subset of the safety set, which will include all patients in the "safety set" except those who have no available efficacy data and/or who do not suffer from type 2 diabetes mellitus from the safety set.

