4. CHANGES IN THE PLANNED ANALYSIS OF THE STUDY

There has been no change in the planned analysis from the statistical methods described in the NIS Protocol.

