6.3 SUBJECT SETS ANALYSED

The following two analysis sets are defined as in NIS Protocol Section 7.3. The safety set will be the basis of all demographic, baseline and safety analyses. Efficacy analysis will be on basis of the efficacy set.

• Safety set:

This patient set includes all patients who had no invalid registration, who were dispensed Trazenta[®] and were documented to have taken at least one dose of Trazenta[®].

• Efficacy set:

This patient set includes all patients with Trazenta[®] in the safety set who have a baseline and at least one available on-treatment HbA1c value.

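### Two SAP exclusion codes (A1.2 and G1.1), applied as written, remove treated patients whom the Protocol keeps or may keep, and no change is declared

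*SAP*

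**What the plan says.** **Safety set.** Protocol 7.3 takes all treated patients "except those who are found to have no observation after enrolment, invalid registration, or invalid contract". SAP 6.3 opens with "The following two analysis sets are defined as in NIS Protocol Section 7.3" and then describes the safety set: "This patient set includes all patients who had no invalid registration", plus Trazenta dispensed and at least one dose documented. It mentions neither a visit nor an observation. SAP 4 states: "There has been no change in the planned analysis from the statistical methods described in the NIS Protocol".

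**Code A1.2** (SAP Table 6.2: 1, under entrance criteria not met) is Trazenta treatment before registration. The exclusion column says All.

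**Registration in the Protocol.** Protocol 3.1 and the flow-chart footnote describe patients already given Trazenta being registered, preferably within 14 days of first administration. Protocol 3.3 counts the day of first administration within those 14 days, and adds that patients registered more than 15 days after starting still enter the safety and efficacy analyses. The inclusion criterion (3.3.2) requires no linagliptin before enrolment.

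**Code G1.1** (same table, under invalid registration) is explained as "Patient made no visit after the entry". The exclusion column again says All.

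**Second AE summary.** SAP 7.8.1 plans two overall AE summaries: one for the safety set and one glossed as all Trazenta-treated patients. Both are also tabulated by SOC and PT. The only added group that the text names for the wider one is patients not on add-on therapy.

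**The concern.** An analysis set for the primary safety endpoint, ADR incidence (SAP 5.1), should follow from the written rules without interpretation. Here it does not, in two places.

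A1.2 treats as a violation what the Protocol describes as normal practice. A programmer who compares first-dose date with registration date would flag the patients whom Protocol 3.3 says to keep.

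G1.1 replaces *observation* with *visit*. Safety information in this surveillance can arrive without a visit. If the two words differ, the exclusion is related to outcome: a patient who dies or is hospitalised elsewhere soon after starting is one who makes no further visit. The event could be on file yet absent from the safety-set ADR and SAE tables, and the SAP does not let a reader tell whether it is shown elsewhere.

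**Working it through.** **A1.2 against the Protocol**

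| Patient | Protocol 3.1 / 3.3 | A1.2 as written |
|---|---|---|
| First dose day 1, registered day 10 | Within the preferred 14 days; kept | Treated before registration; excluded from All |
| First dose day 1, registered day 20 | Outside the preferred period; kept for safety and efficacy | Excluded from All |
| Used linagliptin in the past, restarts it under surveillance | Fails 3.3.2 | Excluded from All |

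Only the third row is a real violation. The documents do not say how many patients are registered after the first dose, so literal application could remove anything from none to all of them.

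**G1.1 against the Protocol**

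Neither document says whether a reported event counts as an observation.

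- *For treating the words as the same:* Protocol 3.1 ties observations to listed time points. Protocol 6.1 does likewise ("The observation time points will be as follows"). Under 6.2.3 the week-156 visit or "the last visit before discontinuation will be the end of the PMS".
- *For treating them as different:* AEs are recorded throughout the observation period (flow chart) and entered in the eCRF when they occur (3.1). SAEs are reported at once by EDC or through a sponsor representative (5.2.2.2, 8.4.1). SAP 7.8.1 merges AE data from a second system. Registration records the start date of administration (6.2.1), so a patient with no later visit can still be documented as treated.

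**The plan's own figure**

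Protocol 7.6 sizes the study at 3,000 patients with at least one observation after treatment. For an ADR of incidence p, P(at least one case) = 1 − (1 − p)^n.

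- p = 0.1%, 95%: n = ln(0.05)/ln(0.999), rounded up = 2,995. At n = 3,000 the probability is 95.03%.
- p = 0.16%: at n = 3,000 the probability is 99.18%.

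The stated 3,000 reproduces.

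**Size of G1.1, illustration only**

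The 10% ADR rate and the values of e, f and K below are assumptions; the documents give none of them.

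1. Overall incidence. Start from 300/3,000 = 10.0% and add e no-visit patients, each with a reported ADR: (300 + e)/(3,000 + e).
   - e = 1: 301/3,001 = 10.03%
   - e = 3: 303/3,003 = 10.09%
   - e = 10: 310/3,010 = 10.30%
2. One rare reaction, exact (Clopper-Pearson) 95% intervals.
   - Case excluded: 0/3,000, interval 0 to 0.12%
   - Case kept: 1/3,001 = 0.03%, interval 0.001% to 0.19%
3. Detection. If a share f of cases falls in excluded patients, P = 1 − (1 − 0.001(1 − f))^3,000.
   - f = 0: 95.0%
   - f = 1%: 94.9%
   - f = 5%: 94.2%
   - f = 10%: 93.3%

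**Why rewording G1.1 alone is not enough**

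Take 3,300 treated patients, of whom K have no visit, with a 10% ADR rate in everyone. The reworded rule is assumed to keep no-visit patients only when they have a reported event.

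| K | G1.1 as written | Reworded only | All treated |
|---|---|---|---|
| 30 | 327/3,270 = 10.0% | 330/3,273 = 10.1% | 330/3,300 = 10.0% |
| 300 | 300/3,000 = 10.0% | 330/3,030 = 10.9% | 330/3,300 = 10.0% |

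Rewording alone adds cases to the numerator without the event-free patients who belong with them.

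**The case against.** **On G1.1.** The SAP calls itself a more technical elaboration of the Protocol (section 3) and says its sets are those of Protocol 7.3. The natural reading is then that G1.1 puts the Protocol condition into operation. Protocol 3.1 comes close to defining observations as visit time points. The list in 6.2.2 that contains adverse events stands under a heading about procedures at selected visits. Discontinuation is itself an observation point, so a reported death would normally generate post-entry data. Final exclusions are decided at report planning meetings before database lock. The wider AE summary, read literally, already covers every treated patient. Serious reactions also reach the authority by expedited reporting (Protocol 8.4.2).

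Most of this stands. A reader might infer that the SAP has been shown to depart from the Protocol, or that fatal events will be lost. The documents support neither: they leave the term open, they do not show that such patients exist, and the wider summary may include them. What remains is that no sentence says a reported event counts as a visit or an observation, and no written rule keeps such a patient. The wider summary names only non-add-on patients as its addition, while G1.1 excludes from All.

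**On A1.2.** The code sits among the entrance criteria and evidently intends the inclusion criterion of no earlier linagliptin. A reader might infer that the SAP would empty the safety set. That is not a fair forecast, because the planning meetings would be expected to catch it. The wording still contradicts Protocol 3.1 and 3.3, and no reading of *registration* in the Protocol removes the conflict.

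**Conclusion.** The point holds at minor severity.

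- A1.2 is wrong as written. It conflicts directly with Protocol 3.1 and 3.3, whatever view is taken of G1.1. The number of patients it would catch is not given.
- G1.1 is an undefined term with a possible outcome-related exclusion, not a proven departure. Its effect on overall ADR incidence is probably small. What matters is a single rare or fatal early event, where one patient separates no case from one case.

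The declaration of no change in SAP 4 is safe only if both codes are read in their intended rather than literal sense. All incidence and detection figures for G1.1 rest on assumed inputs and show scale only; none estimates a bias in this study.

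**What to change.** 1. **A1.2:** limit it to linagliptin use before the treatment start under surveillance, so that registration after the first dose is not a violation.
2. **G1.1:** word it as no post-dose information from any source, and state that a reported AE or death counts as information. If a visit requirement is intended, keep it and declare the change in SAP 4.
3. **Reporting:** give the number of treated patients with no visit after entry, and list any AEs, SAEs and deaths among them.
4. **SAP 7.8.1:** state that the all-treated summary includes G1.1 patients, so that an all-treated denominator stands beside the safety-set one. This should accompany step 2, for the reason shown in the last table of the working.

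The cost is a few changed lines and one short listing, from data already held.

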6.3 SUBJECT SETS ANALYSED

The following two analysis sets are defined as in NIS Protocol Section 7.3. The safety set will be the basis of all demographic, baseline and safety analyses. Efficacy analysis will be on basis of the efficacy set.

• Safety set:

This patient set includes all patients who had no invalid registration, who were dispensed Trazenta[®] and were documented to have taken at least one dose of Trazenta[®].

• Efficacy set:

This patient set includes all patients with Trazenta[®] in the safety set who have a baseline and at least one available on-treatment HbA1c value.

6.5 POOLING OF CENTRES

This section is not applicable because centre is not included in the statistical model.

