3.3 SELECTION OF POPULATION

Planned number of patients to be entered is 3,000.

Patients with renal dysfunction should be entered as listed below:

U13-1769-01

Proprietary confidential information © 2013 Boehringer Ingelheim International GmbH or one or more of its affiliated companies

eGFR <60 mL/min/1.73m²: 140 patients (including 40 patients with \geq 15 mL/min/1.73m² and <30 mL/min/1.73m² and 30 patients with <15 mL/min/1.73m²)

100 elderly patients (≥75 years)

100 patients with hepatic dysfunction should be also entered.

Patients with hepatic dysfunction: >ULN (AST) x1 or >ULN (ALT) x1 or >ULN (Total bilirubin) x1 or >ULN (alkaline phospatase) x1

When both AST and CK increase, patients do not include in hepatic dysfunction.

Sites throughout entire country will be equally listed according the size of the hospitals or general clinics at which Trazenta® tablets are available for prescription.

Number of patients per site is 5-10 patients. Patients will be selected by using the continuous investigation system. The continuous investigation system is commonly used in Japanese PMS and accepted as a patient selection process by the PMDA.

Continuous investigation system is a method of registration that the investigator enrols the patients who will start administration of marketed product into the PMS continuously (without exception) until the requested number of patients is reached.

Preferably, investigators will register patients within 14 days including the day on which the administration of Trazenta[®] Tablets is started. However, patients who are registered over 15 days after starting administration of Trazenta[®] Tablets are also used for safety and efficacy analysis.

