5.1.2 Assessment of efficacy

HbA1c:

The blood samples can be taken at any time and will be measured at the sites by using National Glycohemoglobin Standardization Program (NGSP). Based on the value measured according to the method of the Japan Diabetes Society (JDS), an estimated NGSP value will be calculated by using the following expression.

Estimated NGSP (%) = measured value + 0.4

U13-1769-01

Proprietary confidential information © 2013 Boehringer Ingelheim International GmbH or one or more of its affiliated companies

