7.6 DETERMINATION OF SAMPLE SIZE

The sample size was determined based on the following: To detect an ADR with an incidence of 0.1% (or 0.16%) or greater in at least one patient with a probability of 95% (or 99%) or greater, at least 3,000 patients need to be entered and have at least one observation after treatment. According to the market survey for the patients with DPP-4 inhibitor, it is expected that 2010 patients with sulfonylurea, 1290 patients with biguanide, 840 patients with alpha glucosidase inhibitor, 510 patients with thiazolidinedione, and 90 patients with glinide will be entered, and the incidences of ADR in at least one patient with probability of 95% or greater are 0.15%, 0.24%, 0.36%, 0.59%, and 3.28% respectively.

In addition, according to the request from the Japanese authority, this PMS will target to include elderly patients, patients with renal dysfunction and hepatic dysfunction. The sample size for this patient subset was determined based on the following:

Elderly patients (>75 years)

U13-1769-01

Proprietary confidential information © 2013 Boehringer Ingelheim International GmbH or one or more of its affiliated companies

In a PMS of Micardis[®], an antihypertensive agent, for hypertensive patients (BI Trial No.: 502.511, Specified Drug Use Surveillance of Micardis [U11-1807-01]), 5,602 patients with diabetes mellitus were enrolled. Of the 5602 patients, 46.1% of the patients were <65 years, 33.1% of the patients were 65 to <75 years, and 20.8% of the patients were >=75 years.

Based on this assumption, more than 100 patients are highly likely to be collected in this PMS.

Renal dysfunction

In a PMS of Micardis[®] [U11-1807-01], 4,227 hypertention patients with diabetes mellitus and renal dysfunction were enrolled. According to their eGRF level, 52.4% of the patients were of mild renal dysfunction. 21.4% were moderate, 2.4% were severe, and 1.4% were end-stage, respectively. As this PMS plans to include a total of 3,000 patients, based on the above results of the Micardis[®] surveillance, it is estimated that numbers of patients included in this PMS and with mild, moderate, severe and end stage renal impairment will be about 1,572, 642, 72 and 42patients, respectively.

Based on this assumption, 140 patients with renal dysfunction including 30 end-stage patients are targeted to be included in this PMS.

Hepatic dysfunction

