7.5 SECONDARY ENDPOINT(S)

7.5.1 Key secondary endpoint(s)

This section is not applicable as no key secondary endpoint has been specified in the NIS protocol.

7.5.2 (Other) Secondary endpoint(s)

For the change from baseline in HbA1c at the last observation, descriptive statistics will be calculated by treatment (background medication and total). A 95% confidence interval for the mean change from baseline will also be calculated by treatment (background medication and total).

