7.8 SAFETY ANALYSIS

7.8.1 Adverse events

Unless otherwise specified, the analyses of adverse events (AEs) will be descriptive in nature. All analyses of AEs will be based on the number of patients with AEs and NOT on the number of AEs.

Furthermore, for analysis of AE attributes such as duration, severity, etc. multiple AE occurrence data on the case report form, will be collapsed into AE episodes provided that all of the following applies:

- The same MedDRA lowest level term was reported for the occurrences
- The occurrences were time-overlapping or time-adjacent (time-adjacency of 2 occurrences is given if the second occurrence started on the same day or on the day after the end of the first occurrence)
- Treatment did not change between the onset of the occurrences OR treatment changed between the onset of the occurrences, but no deterioration was observed for the later occurrence

For further details on summarization of AE data, please refer to the guideline 'Handling and summarization of adverse event data for clinical trial reports and integrated summaries' (1).

AE analyses will be carried out after integrating AE data from CRF and AE data from perceive system.

In addition, AEs coded as "no adverse event" will not be included in the AE analyses.

Two overall summaries of AEs will be presented. One will be also made for patients including those who were not treated add-on therapy at baseline (i.e. all patients with Trazenta® treatment). Another one will include patients only with add-on therapy at baseline (i.e. safety set). The frequency of patients with AEs,ADRs, and serious AEs will be also summarised by primary SOC and PT in each patient set.

The frequency of patients with ADRs and with serious AEs will be summarised by treatment (background medication and total), primary SOC and PT. AEs will also be reported by intensity.

To compare risks of overall ADR in different patient subgroups, frequency tabulation stratified by different patient subgroups will be provided with odds ratios and exact 95% confidence intervals whenever specified (see Section 6.4). Logistic regression will be used for odds ratio.

In addition, summaries for the time to onset of first episode for the ADRs will be tabulated, by duration (>0 to 12 weeks, >12 to 26 weeks, >26 to 40 weeks, >40 to 52 weeks, >52 to 64 weeks, >64 to 78 weeks, >78 to 104 weeks, >104 to 130 weeks, >130 to 156 weeks, >156 weeks, unknown), primary SOC, and PT.

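### The 95% CI for the mean HbA1c change makes no allowance for sampling in clusters of 5-10 patients per site, so the overall interval is too narrow if HbA1c change correlates within site

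*SAP*

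**What the plan says.** Protocol 3.3 makes the site the unit through which patients are found: "Number of patients per site is 5-10 patients". Within a site, the physician "enrols the patients who will start administration of marketed product into the PMS continuously (without exception) until the requested number of patients is reached". Protocol 7.6 sets the total: "at least 3,000 patients need to be entered and have at least one observation after treatment".

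On centre, the whole of SAP 6.5 reads: "This section is not applicable because centre is not included in the statistical model". For the HbA1c endpoint, SAP 7.5.2 states: "A 95% confidence interval for the mean change from baseline will also be calculated by treatment (background medication and total"). The supplied text mentions no site term, cluster-robust variance, design effect or ICC.

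For adverse drug reactions (ADRs), SAP 7.4 treats the incidence descriptively and plans no interval for it. The ADR intervals that are planned belong to subgroup comparisons in SAP 7.8.1, which give "odds ratios and exact 95% confidence intervals whenever specified", with the odds ratios from logistic regression. Protocol 7.2 calls all analyses descriptive and exploratory and disclaims formal inference.

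**The concern.** Leaving centre out of the analysis of a mean does not make the patients of one site independent. It leaves between-site variation out of the standard error. An interval built as mean ± 1.96 × SD/√n, which is how SAP 7.5.2 naturally reads, has its stated coverage only if patients within a site are no more alike than patients from different sites.

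There is a plausible reason why they may be more alike. Protocol 4.2.2.1 puts no restriction on concomitant treatment, so the same physician may adjust the other antidiabetic drugs of all 5-10 patients at a site over 156 weeks. Those adjustments act directly on the HbA1c change at last observation.

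At stake is whether the 95% label is correct on the interval for the one efficacy endpoint that Protocol 5.1.1 names. The results go into the reexamination dossier (Protocol 2.1).

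**Working it through.** **The plan's own figure.** Protocol 7.6 derives N = 3,000 from the chance of seeing an ADR at least once, 1 − (1 − p)^n:
- p = 0.1%: 1 − 0.999^3000 = 95.03%; the smallest n for 95% is 2,995.
- p = 0.16%: 1 − 0.9984^3000 = 99.18%.

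Both agree with the protocol. The formula treats patients as independent, and nothing later in the plan relaxes that.

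**Inputs for the HbA1c interval.**
- Patients per site, m: 5 to 10 (Protocol 3.3). Sites: 3,000/10 = 300 to 3,000/5 = 600.
- n = 3,000 (Protocol 7.6). The efficacy set will be somewhat smaller.
- ICC of HbA1c change: not given; assumed 0.01 to 0.10.
- SD of HbA1c change: not given; assumed 1.0 percentage point, range 0.8 to 1.2.

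**Formulas.** Design effect DE = 1 + (m − 1) × ICC. The correct width is √DE times the planned width. Actual coverage of the planned interval is 2Φ(1.96/√DE) − 1.

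| ICC | m = 5: DE, width, coverage | m = 10: DE, width, coverage |
|---|---|---|
| 0 | 1.00, ×1.00, 95.0% | 1.00, ×1.00, 95.0% |
| 0.01 | 1.04, ×1.02, 94.5% | 1.09, ×1.04, 94.0% |
| 0.05 | 1.20, ×1.10, 92.6% | 1.45, ×1.20, 89.6% |
| 0.10 | 1.40, ×1.18, 90.2% | 1.90, ×1.38, 84.5% |

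**Absolute size.** With SD 1.0 the planned half-width is 1.96 × 1.0/√3000 = 0.036 percentage points. At m = 10 it becomes 0.043 for ICC 0.05 (× 1.20) and 0.049 for ICC 0.10 (× 1.38). The largest increase is 0.0493 − 0.0358 = 0.0135, or about 0.01. With SD 0.8 the same worst case goes from 0.029 to 0.040, and with SD 1.2 from 0.043 to 0.059.

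**Intervals by background drug class.** If a class makes up a share s of patients and is spread evenly over sites, a patient shares the site with about (m − 1)s others of that class, so DE ≈ 1 + (m − 1) × s × ICC. The expected numbers in Protocol 7.6 give s = 2,010/3,000 = 0.67 for sulfonylurea and 90/3,000 = 0.03 for glinide. At m = 10 and ICC 0.05:
- sulfonylurea: 1 + 9 × 0.67 × 0.05 = 1.30
- glinide: 1 + 9 × 0.03 × 0.05 = 1.01
- overall: 1.45

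**ADR odds ratios.** These were simulated with 3,000 patients, an assumed 10% ADR rate, a factor present in 30%, m = 5 or 10, an ADR ICC of 0.02 to 0.10 and 2,000 runs per setting. A Wald interval stood in for the exact one.
- Factor unrelated to site: true variance 0.96 to 1.08 times the naive variance; coverage 94.1% to 95.6%.
- Factor strongly clustered by site (factor ICC 0.5): variance ratio 1.03 to 1.44; coverage 89.8% to 95.0%.

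The simulation standard error of a coverage near 95% is √(0.95 × 0.05/2000) = 0.5 points. The first line is therefore hardly distinguishable from nominal coverage.

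**The case against.** Several points on the other side stand.

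- **The ICC is unknown.** A reader might infer that the planned intervals are too narrow as a matter of fact. The documents do not support that. At ICC 0 there is no error, and at ICC 0.01 the shortfall in width is only 2% to 4%.
- **The shared laboratory is a weak mechanism.** Protocol 5.1.2 says HbA1c "will be measured at the sites", which suggests site-level measurement error. But the endpoint is a change from baseline, so a constant site offset cancels. Only drift of the assay or shared treatment practice remains, which makes the upper ICC values less secure.
- **The ADR results are mostly untouched.** A reader might extend the point to the ADR intervals in general. No interval is planned for ADR incidence. Odds ratios for factors that vary within sites are barely affected, and exact intervals tend to be conservative. SAP 6.4, which 7.8.1 cites for the subgroups, is not in the supplied text, so the planned odds ratios cannot be checked and nothing can be held against the plan on that account.
- **The study is descriptive and the effect small.** No test or decision uses the HbA1c interval, and about 0.01 percentage points would not change how the result is read.

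The last point limits the importance of the concern but does not remove it. An interval labelled 95% should have about that coverage in a descriptive report too.

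**Conclusion.** The point holds in conditional form, for the HbA1c interval. The design samples by site, the plan makes no allowance for it, and any positive within-site correlation of HbA1c change makes the overall 95% interval too narrow.

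For an assumed ICC of 0.01 to 0.10 and 5 to 10 patients per site, the shortfall is about 2% to 38% of the width, with actual coverage from about 94.5% down to 84.5%. On the HbA1c scale it is at most about 0.01 percentage points of half-width at an assumed SD of 1.0. By-class intervals are affected less, provided each class is spread over sites; a class concentrated at a few sites would move towards the overall figure.

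The general claim that the ADR intervals are too narrow is not supported. It could apply only to odds ratios for factors that themselves cluster by site. Inpatient or outpatient status is a plausible example, because Protocol 3.3 draws on both hospitals and general clinics.

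This is a cheap improvement in the accuracy of a stated precision and does not threaten the study's conclusions.

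**What to change.** - **SAP 6.5:** replace the current sentence with, for example: *Site is the sampling cluster. No site effect is fitted, but the variance of the mean HbA1c change takes clustering by site into account (see 7.5.2).*
- **SAP 7.5.2:** add: *The 95% confidence interval uses a robust variance with site as cluster (for example PROC SURVEYMEANS with a CLUSTER statement for site), overall and by background medication. The observed intra-site correlation of HbA1c change is reported.*
- **SAP 7.8.1:** keep the exact intervals for the ADR odds ratios. Large-sample robust intervals are less reliable when ADRs are sparse in a stratum, so replacing the exact ones would be a trade-off. Add a site-clustered interval as a sensitivity analysis only for factors that cluster by site, such as inpatient or outpatient status.

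**Cost:** a few lines of SAP text and one statement in the program. Site is already recorded at registration (Protocol 6.2.1), and 300 to 600 clusters are enough for a robust variance to behave well. The point estimate does not change. The downside is a slightly wider interval; if the ICC is near zero, the interval stays essentially as planned.
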